The subjects in this study will include adults with GI adenocarcinomas with no available standard or curative treatments.

TREATMENT

MEDI-565 will be administered by IV infusion over 3 hours per day for 5 consecutive days every 28 days (1 cycle). The starting dose was 0.75 µg.

The proposed dose levels for MI-CP216 are 0.75µg, 2.25 µg, 6.75µg, 20 µg, 60 µg, 120 µg, 300 µg, 750 µg, 1.5mg, 3 mg, 5 mg, 7.5 mg, and 10 mg.

Treatment may be continued in subjects who have a response of stable disease (SD) or better until documentation of disease progression, initiation of alternative anticancer therapy, unacceptable toxicity, or other reasons for treatment withdrawal.

Beginning with Amendment 4, subjects will receive inpatient administration of MEDI-565 starting with Cycle 1, Day 1 until completion of the infusion on Cycle 1, Day 2 and again beginning with the infusion on Cycle 1, Day 4 until completion of the infusion on Cycle 1 Day 5. Subsequent infusions of MEDI-565 will be administered to subjects on an outpatient basis.

In the dose-expansion phase, 3 treatment arms of approximately 20 subjects with refractory pancreatic adenocarcinoma, 20 subjects with refractory CRC, and 20 subjects with refractory gastroesophageal cancer may be enrolled and receive MEDI-565 at the MTD/OBD dose by IV infusion over 3 hours per day for 5 consecutive

days every 28 days. Commencement of the dose-expansion phase and the selection of any tumor types will be based on any previously observed signal of antitumor activity and the safety profile of MEDI-565 emerging from the dose-escalation phase.

ASSESSMENT OF ENDPOINTS

Primary Endpoints

The number (percentage) of subjects with a DLT will be summarized by dose level and overall. The MTD evaluation will be based on the evaluable population for DLT and is defined as the highest dose, up to 10 mg, where the DLT frequency is less than 33%.

The OBD will be determined based upon analysis of all available subject data including safety, PK, pharmacodynamic, biomarker, and antitumor activity data.

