administration prior to MEDI-565 administration and additional blood pressure, heart rate, and pulse oximetry monitoring during and following administration of MEDI-565. To minimize risk to subjects, Amendment 4 of Study MI-CP216 will re-start dosing at the next previously lower dose of 1.5 mg (ie, 1 dose level below the level at which the hypoxia events were observed) with implementation of the additional risk mitigation measures outlined above for all new subjects. A dose of 1.5 mg was chosen to re-start the study because it was judged to be more conservative from a safety standpoint and consistent with standard practice to de-escalate one dose level below the dose level (ie, 3 mg) at which the DLTs of hypoxia were observed. Provided no more than 1 out of 6 subjects experience DLTs in the preceding cohort, dose escalation is planned to continue in sequential fashion and re-evaluate the 3 mg dose (Cohort 12) followed by 5 mg (Cohort 13), 7.5 mg (Cohort 14), and 10 mg (Cohort 15) doses.

MEDI-565 will be administered by IV infusion over 3 hours per day for 5 consecutive days (ie, Days 1 through 5) every 28 days (defined as 1 cycle). Subjects in the dose-escalation phase are considered evaluable if they receive at least 1 full cycle of MEDI-565 and complete the safety follow-up through the DLT evaluation period of 28 days after the first dose of MEDI-565, or experience any DLT as defined in Section 4.5.4.5. Subsequent cycles may be delayed for up to 7 days for management of some types of toxicity (Section 4.5.4.4) or to accommodate scheduling issues. Nonevaluable subjects, defined as any subject discontinued during the DLT evaluation period for reasons other than a DLT, will be replaced in the same dose cohort. No intra-subject dose escalation will be allowed.

Dose escalation will continue until the MTD or a maximum dose of 10 mg is reached. In the event that no DLTs are observed during dose escalation and significant antitumor activity is observed, the Sponsor may halt dose escalation prior to determining the MTD provided that PK, pharmacology, safety and preliminary antitumor activity data support the use of an OBD below the MTD. On determination of the MTD or OBD, additional subjects will be enrolled so that a total of 6 subjects receive the MTD/OBD during the dose-escalation phase.

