Once the MTD or OBD is determined, a total of 60 additional subjects (20 each with refractory pancreatic adenocarcinoma, refractory CRC, or refractory gastroesophageal cancer) may be enrolled at MTD or OBD in a dose-expansion phase. Commencement of the dose-expansion phase and the selection of any tumor types will be based on any previously observed signal of antitumor activity and the safety profile of MEDI-565 emerging from the dose-escalation phase. Subjects in the dose-expansion phase will receive MEDI-565 at the MTD or OBD as a 3-hour IV infusion per day for 5 consecutive days every 28 days (defined

as 1 cycle). Subjects in the dose-expansion phase are considered evaluable for antitumor activity if they receive at least 2 full cycles of MEDI-565 or discontinue due to progressive disease or toxicity. Nonevaluable subjects in the dose-expansion phase will be replaced. All subjects who receive any amount of MEDI-565 will be considered evaluable for safety.

A study flow diagram is shown in [Figure 3.1-1](#).

[figure not shown]

Figure 3.1-1 Study Flow Diagram

CRC = colorectal cancer; MTD = maximum tolerated dose; OBD = optimum biologic dose

The endpoints to be measured in this study are described in Section 7.3.

Standard 3+3 design for study enrollment is shown in [Figure 3.1-2](#).

[figure not shown]

Figure 3.1-2 Standard 3+3 Flow Diagram

DLT = dose-limiting toxicity; MTD = maximum tolerated dose; OBD = optimum biologic dose

The diagram above shows the work flow of a standard “3+3” design. A dose-escalation trial enrolls a group of 3 subjects at dose level X. If no subject experiences a DLT, escalate to the next higher dose level, X+1. If 2 or more subjects experience a DLT, stop dose escalation. If 1 subject experiences a DLT, expand dose level X to a total of 6 evaluable subjects. If 1 of 6 experiences DLT, escalate to dose level X+1. If 2 or more of 6 experience DLT, stop dose escalation. If the study stops at dose level X, then the MTD is estimated as the prior dose level (X-1).

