4.5.4.2 Dose Escalation

Rules for dose escalation are as follows:

- 1) The MTD will be determined based on the assessment of a DLT (refer to Section [4.5.4.5](#)) during the DLT period, which is defined as the time from the first dose of MEDI-565 to 28 days after the first dose of MEDI-565 (Cycle 1). Subjects are considered evaluable for assessment of DLT if they receive at least 1 full cycle of MEDI-565 (Days 1-5, Cycle 1) and complete the safety follow-up (Days 6-28, Cycle 1) through the DLT evaluation period or experience any DLT. Nonevaluable subjects will be replaced.
- 2) If a Grade 3 or greater AE or toxicity corresponding to a DLT occurs in any cohort, that cohort will be expanded to 6 evaluable subjects. If 1 of 6 subjects experiences a DLT in the expanded cohort, dose escalation will proceed to the next dose level. If ≥ 2 subjects experience a DLT in a given cohort, the MTD will have been exceeded and the next lower dose will be evaluated as the MTD. The MTD will be defined as the highest dose, up to 10 mg, at which no more than 1 out of 6 subjects experience a DLT.
- 3) If the MTD is exceeded during dose escalation (≥ 2 out of 6 subjects experience a DLT in a given cohort), and the prior lower dose level is demonstrated to be safe (≤ 1 out of 6 subjects with DLTs), an intermediate dose may be evaluated if appropriate based on available PK, pharmacodynamics, safety, and clinical data. Dose escalation must stop prior to reaching the dose and exposure for the cohort that exceeded the MTD.
- 4) If significant antitumor activity is observed during dose escalation prior to identifying an MTD and before reaching the 10 mg dose, the Sponsor may halt dose escalation without determining the MTD. In this case, an OBD below the MTD may be chosen for the dose-expansion phase of the study, provided this is supported by the safety, antitumor activity, PK, pharmacodynamic, and biomarker data.

A study-specific Dose Escalation Committee will provide ongoing safety surveillance of the study, with regularly scheduled reviews of safety and other relevant data. This committee will be responsible for dose-escalation decisions and making recommendations regarding further conduct of the study. The sponsor will notify sites when enrollment into each dose cohort has been completed and when enrollment into the next dose cohort is permitted. In addition, MedImmune's internal safety monitoring committee (ie, SMC or equivalent), provides safety

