7.2 Analysis Populations

The Evaluable Population for DLT includes all subjects enrolled in the dose-escalation phase who received at least one full cycle of MEDI-565 and completed safety follow-up through the DLT evaluation period (defined in Section 4.5.4.5) or experience any DLT. The Evaluable Population for DLT will be used for the MTD evaluation.

The Safety Population includes all subjects who receive any investigational product.

The Per-Protocol Population will include all subjects who complete 2 cycles of treatment or discontinue treatment due to disease progression or toxicity.

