7.3 Endpoints

7.3.1 Primary Endpoints

The primary endpoints are as follows:

- The number (percentage) of subjects with a DLT will be summarized by dose level and overall. The MTD evaluation will be based on the evaluable population for DLT.
- The OBD will be determined based upon analysis of all available subject data including safety, PK, pharmacodynamic, biomarker, and antitumor activity data.
- The number (percentage) of subjects with AEs and SAEs reported through 30 days after the last dose of MEDI-565 will be summarized for all subjects who received at least one dose of study drug (Safety Population). Adverse events and SAEs will be graded according to the [NCI CTCAE v4.03](#) and described by system organ class using the Medical Dictionary for Regulatory Activities (MedDRA) preferred term, severity, and relationship to MEDI-565. Frequency rates will be calculated for each system organ class and MedDRA preferred term.
- The number (percentage) of subjects with significant or important clinical findings in ECG will be summarized by dose cohort.
- The number (percentage) of subjects who had clinically significant laboratory changes recorded as AEs will be summarized. Laboratory hematology and chemistry values will be summarized with the worst value during the study by dose cohort. Clinically significant coagulation profile and urinalysis results will be described.

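### The MTD population, the DLT summary and the six-subject requirement were not updated for dexamethasone prophylaxis, so 1.5 mg and 3 mg each mix two regimens

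*Protocol*

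**What the plan says.** **Stopping rule.** Protocol section 4.5.4.2, rule 2, states: "If ≥ 2 subjects experience a DLT in a given cohort, the MTD will have been exceeded". The text under Figure 3.1-2 in section 3.1 says of the first three subjects at a dose: "If 2 or more subjects experience a DLT, stop dose escalation". Neither names a regimen or an amendment.

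**MTD definition.** Rule 2 takes the highest dose up to 10 mg "at which no more than 1 out of 6 subjects experience a DLT". The Study Abstract (Primary Endpoints) says that the MTD "is defined as the highest dose, up to 10 mg, where the DLT frequency is less than 33" per cent.

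**MTD population and summary.** Section 7.2: "The Evaluable Population for DLT includes all subjects enrolled in the dose-escalation phase" who are evaluable, and "The Evaluable Population for DLT will be used for the MTD evaluation". Section 7.3.1: "The number (percentage) of subjects with a DLT will be summarized by dose level and overall".

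**Six-subject requirement.** Section 3.1: once the MTD or OBD is determined, "additional subjects will be enrolled so that a total of 6 subjects receive the MTD/OBD during the dose-escalation phase".

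**Regimen.** Table 4.5.2-1 gives 1.5 mg in Cohort 9 (3 subjects) and again in Cohort 11 (3 to 6), and 3 mg in Cohort 10 (5 subjects) and again in Cohort 12 (3 to 6). Its footnote assigns dexamethasone prophylaxis to Cohort 11 and higher and to the expansion cohorts. Sections 1.4, 3.1 and 3.4 explain that Cohort 10 had 2 DLTs of hypoxia in 5 subjects, and that Amendment 4 restarts at 1.5 mg and then re-evaluates 3 mg, with prophylaxis and closer monitoring.

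**The concern.** The prophylaxis was added to prevent the kind of event that limited dosing in Cohort 10, and it is given around the first infusion, inside the 28-day DLT period. A DLT rate without it and a DLT rate with it are therefore estimates of different quantities. Every subject in the expansion phase, up to 60, receives it.

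The two doses that were given both ways are also realistic candidates for the MTD. If 5 mg is not tolerated, 3 mg is the candidate. If 3 mg fails again, 1.5 mg is the candidate. In those cases the primary DLT result at the candidate dose would be reported on a mixture. The count of 6 subjects meant to support that dose could also be reached partly with subjects on a regimen that is no longer used. Section 4.5.4.3 makes the MTD a ceiling for the expansion dose. If 5 mg or more qualifies as the MTD, the mixture does not affect the chosen dose.

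**Working it through.** **1. The plan's own counts (section 7.5).** The minimum for escalation is 4×1 + 5×3 + 5 + 5×3 = 39. The maximum is 4×1 + 5×3 + 5 + 5×6 = 54. Adding 60 gives 99 and 114. All four figures reproduce.

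**2. Who stands behind each dose level** (Table 4.5.2-1 and its footnote):

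| Dose | Without mandated prophylaxis | With prophylaxis | Total at the dose level |
|---|---|---|---|
| 1.5 mg | Cohort 9: 3 | Cohort 11: 3 to 6 | 6 to 9 |
| 3 mg | Cohort 10: 5 | Cohort 12: 3 to 6 | 8 to 11 |

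A summary by dose level, in the population defined in 7.2, uses the last column.

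**3. The six-subject requirement at 1.5 mg.** Suppose Cohort 11 has 0 DLTs in its first 3 subjects and escalation proceeds. Suppose Cohort 12 then has 2 or more DLTs. The candidate MTD is 1.5 mg. Cohort 9 (3) plus Cohort 11 (3) is 6, so the sentence in 3.1 is already met with 3 subjects on the expansion regimen.

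With 0 DLTs in n subjects, the one-sided exact 95% upper limit for the DLT rate is 1 − 0.05^(1/n):
- n = 3: 1 − 0.05^(1/3) = 0.632, or 63%
- n = 6: 1 − 0.05^(1/6) = 0.393, or 39%

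**4. The two MTD definitions.** At 6 subjects they agree: 1/6 (16.7%) passes both and 2/6 (33.3%) fails both. At the combined denominators of 9 and 11 they need not agree. The figures below are illustrations only. They read 1 out of 6 as a proportion, which the protocol does not do.

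For 3 mg, the combined result depends on how many Cohort 10 events still count as DLTs:

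| Cohort 10 events counted | Cohort 12 at 0/6 | Cohort 12 at 1/6 |
|---|---|---|
| 0 | 0/11 (0%) | 1/11 (9.1%) |
| 1 | 1/11 (9.1%) | 2/11 (18.2%) |
| 2 | 2/11 (18.2%) | 3/11 (27.3%) |

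Every entry is below 33%. Those at 18.2% and 27.3% are above 16.7%.

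For 1.5 mg, Cohort 11 at 2/6 fails rule 2. Combined with an assumed 0/3 in Cohort 9 it is 2/9 (22.2%), which is below 33%.

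**The case against.** The strongest reply is that the cohort is the unit of decision. Rules 2 and 3 refer to a given cohort, section 3.1 conditions each step on the preceding cohort, and section 4.5.4.3 refers the MTD to section 4.5.4.2. Sections 1.4, 3.1 and 3.4 attribute the finding that 3 mg exceeded the MTD to earlier protocol versions, and plan the retest openly and with reasons. This stands. A reader might infer from rule 2 that Cohort 10 bars 3 mg under the current text. The documents do not support that reading, because the explicit Amendment 4 plan governs conduct.

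A reader might also infer that the combined rates in step 4 would decide the MTD. That is not supported either. No section says that Cohorts 10 and 12, or 9 and 11, are combined for the decision. The 0/3 for Cohort 9 is inferred from its size and the escalation that followed. Whether both Cohort 10 events would still be DLTs under the current exception for infusion-related events that resolve within 12 hours (4.5.4.5) cannot be determined from the text shown.

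Finally, section 7.1 leaves analysis detail to the SAP, and a DLT table could be split by regimen there. That answers part of the point about the table. It does not settle the six-subject sentence, which directs enrolment, or the MTD population and the two MTD definitions, which the protocol itself fixes. The Dose Escalation Committee could ask for more subjects at 1.5 mg, but nothing in 3.1 requires it to.

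**Conclusion.** The point holds for reporting and for the evidence behind the chosen dose, not for the conduct of escalation. Taken literally, sections 7.2 and 7.3.1 and the abstract yield DLT rates at 1.5 mg and 3 mg that mix subjects without and with prophylaxis. The six-subject requirement can be met at 1.5 mg with only 3 subjects on the regimen used in expansion, where a clean result leaves an upper limit of 63% instead of 39%.

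This rests on the cohort sizes and footnote of Table 4.5.2-1 and on the six-subject sentence naming no regimen. The upper limits assume no DLTs among the subjects counted. No change in exposure during escalation is claimed. The gap affects dose selection only if the MTD falls at 1.5 mg or 3 mg. The change should be made, preferably before results from Cohorts 11 and 12 are known, so that the denominator is not chosen afterwards.

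**What to change.** By amendment:
- **3.1:** require that 6 subjects receive the MTD or OBD with dexamethasone prophylaxis.
- **4.5.4.2 and 7.2:** state that the MTD decision is made per cohort on Cohorts 11 and above and any added cohort, and that Cohorts 1 to 10 are reported separately.
- **7.3.1 and Study Abstract:** summarize DLTs by dose level and regimen.
- **Study Abstract:** replace the 33% threshold with rule 2's limit of 1 in 6.

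Leaving Cohorts 1 to 10 out of the MTD evaluation is a substantive choice. The reason is that they lacked the prophylaxis every later subject receives. If the sponsor prefers to count them, the protocol should say so and give the threshold for combined cohorts.

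The cost is a few sentences and at most 3 more subjects at 1.5 mg. These fall within the 3 to 6 planned for Cohort 11, so the ranges of 39 to 54 and 99 to 114 hold. Doses and procedures do not change.

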4.5.4.3 Dose Expansion

During the dose-escalation phase, the MTD will be determined as described in Section 4.5.4.2 or an OBD will be selected as determined by available PK, IM, biomarkers, safety, and available antitumor activity data. The selected dose for the dose-expansion phase will not exceed the MTD nor the highest dose tested in the dose-escalation phase.

4.5.4.4 Dose Modification for Toxicity Management

Management of Dose Interruption During Infusion

The MEDI-565 infusion will be stopped immediately for the following events:

- The subject experiences a DLT as defined in Section 4.5.4.5
- The subject meets criteria for temporary or permanent discontinuation of MEDI-565 as described in Section 4.2.3
- The investigational product is incorrectly prepared or administered (eg, overdose)
- There is a technical problem with the infusion pump

The MEDI-565 infusion may be restarted according to the criteria listed below:

- If the MEDI-565 infusion is interrupted for reasons other than toxicity, it can be restarted at the same dose with no additional measures required
- If the MEDI-565 infusion is interrupted for management of toxicity, it may be restarted according to the guidelines in Table 4.5.4.4-1

Dose Modification Following the DLT Period

Following the DLT period, any unacceptable toxicity (as defined by the DLT criteria) will result in the discontinuation of MEDI-565; subjects who have DLT-like events after the DLT period will not be retreated with MEDI-565. Exceptions to this may occur on a case-by-case basis for subjects who have experienced clinical benefit and whose unacceptable toxicity resolves within 7 days. Decisions to retreat such subjects will be made in conjunction with the FDA.

For other toxicities observed following completion of the DLT period, subsequent cycles of MEDI-565 may be delayed or modified as described in [Table 4.5.4.4-1](#). Both hematologic and nonhematologic toxicities will be graded according to [NCI CTCAE v4.03](#).

Table 4.5.4.4-1 MEDI-565 Dose Modification Table (Cycle 2 and Greater)

Hematologic or Nonhematologic Toxicity	Dose Modification of MEDI-565
≤ Grade 1	None
Grade 2	
For AEs occurring during treatment with MEDI-565, do not stop infusion. The infusion may be slowed but must be completed within 6 hours. Grade 2 hypotension, pyrexia or chills that do not respond to medical therapy and do not allow completion of the infusion within 6 hours will result in permanent discontinuation of MEDI-565.
 
For AEs present at the end of the treatment cycle, delay next cycle of MEDI-565 for up to 7 days until resolution to ≤ Grade 1 or baseline, and resume at current dose level.
 
If AE does not resolve to ≤ Grade 1 or baseline within 7 days of the end of the cycle, initiate next cycle at 50% of current dose level.

Table 4.5.4.4-1 MEDI-565 Dose Modification Table (Cycle 2 and Greater)

Hematologic or Nonhematologic Toxicity	Dose Modification of MEDI-565
Grade 3 or 4	
First Occurrence^a :
 
Discontinue MEDI-565 if toxicity meets the criteria for DLT as defined for the first cycle of treatment (see Section, 4.5.4.5) including Grade 3 or 4 cytokine release syndrome or allergic reactions. Subjects who experience a Grade 3 or 4 toxicity that meets DLT criteria that resolves within 7 days (except cytokine release syndrome or allergic reaction) and who are demonstrating clinical benefit may be allowed to continue receiving MEDI-565 following consultation with FDA.
 
For Grade 3 or 4 toxicities that do not meet DLT criteria and resolve to Grade 1 or baseline within 7 days MEDI-565 may be continued at 50% of current dose level.
 
For acute infusion reactions, AEs will be treated symptomatically and the rate of infusion may be slowed. If infusion is completed within 6 hours, subsequent doses of MEDI-565 may resume at 50% of current dose level. If infusion is not completed within 6 hours, discontinue MEDI-565.
 
Second Occurrence^a :
 
Discontinue MEDI-565.

^a Refers to the first or second occurrence of a Grade 3 or 4 toxicity in a given subject, at any dose level, for any cycle after Cycle 1

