4.2.3 Withdrawal Criteria

An individual subject will not receive any further investigational product if any of the following occur in the subject in question:

- 1) Withdrawal of consent or lost to follow-up
- 2) Any AE, that, in the opinion of the investigator or the sponsor, contraindicates further dosing
- 3) Subject is determined to have met one or more of the exclusion criteria for study participation (such subjects will be replaced if identified during the DLT period in the dose-escalation phase or at any point in the expansion phase)
- 4) Pregnancy or intent to become pregnant (see Section 6.4.3.3)
- 5) Documentation of PD
If radiographic changes are believed by the investigator to be secondary to drug induced inflammation and not tumor progression, the investigator may postpone a diagnosis of PD until the next scheduled radiographic evaluation in the study (Wolchok et al, 2009).
- 6) Subject noncompliance
- 7) Initiation of alternative anti-cancer treatment
- 8) Treatment with another investigational agent
- 9) Dose-limiting toxicity (see Section 4.5.4.5 for definition of DLTs)
- 10) After Cycle 1 (protocol-defined DLT period), any events of unacceptable toxicity (as defined by DLT criteria). Exceptions to this may be granted on a case-by-case basis

for subjects who are receiving clinical benefit and whose unacceptable toxicity resolves within 7 days, and must be agreed to in conjunction with the FDA (see Section 4.5.4.4)

- 11) After Cycle 1 (protocol-defined DLT period), any events where MEDI-565 treatment is interrupted and a cycle is delayed more than 7 days for reasons of toxicity, or treatment is delayed more than once during the study (see Section 4.5.4.4)
- 12) Occurrence of an acute infusion reaction or cytokine release syndrome resulting in pyrexia, chills, or NCI CTCAE v4.03 Grade 2 hypotension that does not allow for the completion of the infusion within 6 hours from the start of the infusion despite a slowing of the infusion rate or treatment with fluids, antihistamines, or steroids
- 13) Occurrence of a Grade 3 or greater event as a component of the cytokine release syndrome
- 14) Occurrence of a suspected immunoglobulin E (IgE)-mediated allergic reaction (ie. presence of urticaria or bronchospasm)
- 15) Significant medical events that in the opinion of the medical monitor or investigator warrant subject discontinuation.

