In the event of an infusion-related reaction, the infusion of MEDI-565 may be decreased by 50% or interrupted until resolution of the event (up to 4 hours) and reinitiated at 50% of the initial rate until completion of the infusion. Acetaminophen and/or an antihistamine (eg. diphenhydramine) may be administered at the discretion of the investigator as long as liver function tests (LFTs) are within normal limits. If the infusion reaction is severe or prolonged, glucocorticoids (dexamethasone 8 mg every 8 hours, or equivalent, or by standard

institutional practice) should be administered as well following best medical practice. For subsequent infusions in subjects who experience an infusion reaction and do not require discontinuation of MEDI-565 (see [Table 4.5.4.4-1](#)), acetaminophen and an antihistamine may be administered prior to initiation of the MEDI-565 infusion.

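### For a Grade 2 suspected IgE-mediated reaction in Cycle 2 or later, the Grade 2 row of Table 4.5.4.4-1 contradicts withdrawal criterion 14 and the stop list in Section 4.5.4.4

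*Protocol*

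**What the plan says.** Section 4.2.3 opens its withdrawal criteria with "An individual subject will not receive any further investigational product if any of the following occur in the subject in question". Criterion 14 reads: "Occurrence of a suspected immunoglobulin E (IgE)-mediated allergic reaction (ie. presence of urticaria or bronchospasm". It sets no grade threshold and no cycle limit.

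Section 4.5.4.4 begins with a stop list: "The MEDI-565 infusion will be stopped immediately for the following events". One item on it is "The subject meets criteria for temporary or permanent discontinuation of MEDI-565 as described in Section 4.2.3". The restart rule just below lets an infusion interrupted for toxicity resume under Table 4.5.4.4-1.

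That table, titled for Cycle 2 and greater, says in its Grade 2 row: "For AEs occurring during treatment with MEDI-565, do not stop infusion". It continues: "The infusion may be slowed but must be completed within 6 hours". The row then makes one exception, permanent discontinuation for Grade 2 hypotension, pyrexia or chills that resist treatment and prevent completion in that time. Allergic reactions appear only in the Grade 3 or 4 row, among toxicities that lead to discontinuation: "including Grade 3 or 4 cytokine release syndrome or allergic reactions".

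Section 4.5.4.1 allows acetaminophen and an antihistamine before "subsequent infusions in subjects who experience an infusion reaction and do not require" discontinuation. For who must discontinue, it cites the table and not Section 4.2.3.

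**The concern.** A site managing Grade 2 urticaria or bronchospasm during a Cycle 2 infusion would naturally look at the dose modification table. For that event the table gives the opposite order to the withdrawal criterion. Following it would keep MEDI-565 running in a subject who should receive no more.

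The protocol takes the risk seriously. Section 4.5.4.1 expects that allergic reactions can occur and requires readiness for anaphylaxis. Section 1.4 lists bronchospasm and urticaria among serious, sometimes fatal, hypersensitivity reactions to an approved anti-CD3 antibody. Under Section 4.5.2, infusions from Cycle 2 onward are given to outpatients, so the bedside instruction should be unambiguous.

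**Working it through.** The protocol gives no figure on this point to reproduce, and the check is mainly textual. Take Grade 2 urticaria, suspected to be IgE-mediated, during a Cycle 2 infusion.

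| Rule | Instruction for this event |
|---|---|
| Section 4.2.3, criterion 14 | No further MEDI-565 |
| Section 4.5.4.4, stop list | Stop at once, because a Section 4.2.3 criterion is met |
| Table 4.5.4.4-1, Grade 2 row | Do not stop; slow if needed; finish within 6 hours |

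The first two agree and the third conflicts with both.

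**Does the table reach this event?** Its introductory sentence covers toxicities other than those meeting DLT criteria, and does not remove events covered by Section 4.2.3. That sentence speaks of later cycles, but the Grade 2 row itself gives an order for events during treatment. So the row applies.

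**Is the missing grade in criterion 14 an oversight?** Criteria 12 and 13 each state a CTCAE grade (Grade 2 for hypotension, Grade 3 or greater for a component of cytokine release syndrome). Criterion 14 does not, so on its face it covers Grade 2.

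**Do the cross-references settle it?** No. The restart rule does not separate temporary from permanent discontinuation, so a correctly stopped infusion is referred back to the row that says to finish it. Section 4.5.4.1 makes the same table the reference for discontinuation. Naming allergic reactions only at Grade 3 or 4 suggests that Grade 2 events may continue.

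**Illustrative size.** Inputs: a 3-hour infusion (Section 4.5.2); doses of 1.5 to 10 mg under Amendment 4 (Table 4.5.2-1). Assumptions: constant rate, saline flush ignored, onset at t hours. The protocol gives no onset times, so t is shown over a range.

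Share of the day's dose still to be given = (3 − t)/3:

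- t = 0.5: 2.5/3 = 83%, or 1.25 mg (of 1.5) to 8.3 mg (of 10)
- t = 1.5: 1.5/3 = 50%, or 0.75 to 5 mg
- t = 2.5: 0.5/3 = 17%, or 0.25 to 1.7 mg

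Under criterion 14 the share is 0%.

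**Does the 6-hour limit catch this?** Not if the infusion is only slowed. At the half rate allowed in Section 4.5.4.1, it ends at t + 2(3 − t) = 6 − t hours: 5.5, 4.5 and 3.5 hours for the three onsets, all within the limit. If it is first interrupted for d hours, it ends at 6 − t + d and passes the limit only when d exceeds t. Even then, the row's discontinuation clause names only hypotension, pyrexia and chills.

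**The case against.** The strongest reply is that the protocol already settles the matter. Criterion 14 is specific and absolute. The stop list is mandatory, names Section 4.2.3 and comes before the table in the same section. The table's introduction is permissive and concerns later cycles, and a withdrawn subject has none. Section 4.5.4.1 lets an infusion be interrupted for up to 4 hours for an infusion-related reaction, and criteria 2 and 15 allow dosing to end on medical judgement. The case is also narrow: Cycle 2 or later, exactly Grade 2, during infusion, and suspected IgE-mediated. Section 4.5.4.1 does not list urticaria or bronchospasm among the most frequent acute drug-related signs.

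Most of this stands. Stopping is the better reading, and a site is not left with the Grade 2 row alone. What remains is that the row gives a literal contrary order, nothing states precedence, and two cross-references point to the row.

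Three stronger readings are tempting but not supported:

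- That the row ignores Section 4.2.3 altogether. It does not, since it restates criterion 12. The gap is criterion 14. Repeating one infusion-related criterion and not the other does, however, make the row look complete.
- That the Grade 1 row conflicts as well. It says only that no dose modification is needed, which is silence on stopping and not an order to continue.
- That the dose shares measure risk. They are arithmetic on assumed onset times. The protocol gives no incidence of these reactions, so no number of affected subjects can be stated.

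**Conclusion.** The contradiction is real for one case: a Grade 2 suspected IgE-mediated reaction during an infusion in Cycle 2 or later. It is a stated instruction that is wrong for that event, and more than a missing detail. Because Section 4.2.3 and the stop list point the right way, it is a narrow wording conflict on patient safety, worth correcting at the next amendment.

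A reader might infer that DLT counts or the MTD are affected. They are not. DLTs are assessed in Cycle 1, the table by its title starts at Cycle 2, and sample size and error rates do not depend on this text. The 83% to 17% range describes exposure in a single infusion if the row were followed. It rests on a constant rate and assumed onset times.

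**What to change.** - Open the Grade 2 row with an exception: for suspected IgE-mediated reactions (urticaria or bronchospasm) of any grade, the infusion stops at once and MEDI-565 is permanently discontinued, citing Section 4.2.3, criterion 14.
- Limit the restart rule in Section 4.5.4.4 to subjects who do not meet a permanent-discontinuation criterion in Section 4.2.3.
- Cite Section 4.2.3 beside the table in Section 4.5.4.1.

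The override should be confined to criterion 14. A blanket statement that every Section 4.2.3 event overrides the table would cancel the case-by-case retreatment agreed with FDA under criterion 10 and the Grade 3 or 4 row, which should stay as it is.

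The cost is three short text edits in the next amendment, with no added visits, data or subjects.
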